10.5.6 Missing Data

The impact of missingness in the covariates will be evaluated in several ways. Multivariable models will be based on complete case analyses. The robustness of the complete case analyses will be evaluated by comparing key baseline characteristics between the full dataset and the complete case dataset. Additionally, unadjusted outcome results will be compared between the two datasets. Multiple imputation methods will be utilized to complete baseline missingness, and these baseline-adjusted results will be compared to the complete case adjusted results. The proposed mixed models for repeated measures are valid under the missing at random mechanism (MAR) to address missingness in the PRO. The pattern of missingness in PRO will be assessed to evaluate the MAR assumption.

If data from questionnaires are missing, when possible, the reason for the missing data will be categorized and documented as follows:

- subject felt too ill
- clinician or nurse felt the subject was too ill
- subject felt it was inconvenient or took too much time
- subject felt it was a violation of privacy
- subject didn't understand the actual language or was illiterate
- administrative failure to distribute the questionnaire
- not required at this time point
- other, specify
- unknown

10.5.7 Exploratory Analysis

Heterogeneity of Treatment Effects: We will evaluate the consistency of the intervention across site and patient level characteristics. The heterogeneity of treatment effects (HTE) will be evaluated using potential treatment effect modifiers measured prior to randomization. Site level factors will include cluster size (large vs small) and urban vs rural sites, while subject level factors are those previously listed in the multivariable modeling description. For each factor, subgroup analysis will be conducted on each of the mutually exclusive factor levels. Evaluation of the HTE will be performed qualitatively by comparing the treatment group differences across the factor levels. More formally, each subject-level factor will be evaluated using models to include treatment arm, the baseline factor, and the treatment by factor interaction.

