10.2 Sample Size and Accrual

Sample size calculations are based on the primary endpoint of acute care utilization visits per year (at the EA-SCD participant level). Utilizing a randomized cluster design, seven clinical sites will be randomized per arm. The sample size calculation strategy is to calculate the required minimum sample size based on an individual patient randomized design, and then inflate the sample size based on cluster randomized considerations.⁵⁴ A conservative estimate of the average acute care utilization rate for EA-SCD is 6 acute care visits per year based on data for North Carolina reported by the RuSH population surveillance project.⁴ In South Carolina, the acute care utilization rates among 18-30 y with SCD was reported as 7.17 (95% CI 6.34-7.99).55 At Atrium Health (formerly known as Carolinas Healthcare System), 295 EA-SCD had 1972 emergency department visits and 221 hospital admissions in 2015 with an average acute care

utilization rate of 6.82 visits per year. This study is designed to detect a 20% reduction in the number of acute care encounters per year (assuming a base case of 6 encounters). A 20% reduction in acute care utilization is considered clinically significant based on patient partners reporting that 1 less acute care visit a year is meaningful. Based on a two- sided alpha = 0.05significance level, 67 EA-SCD participants per arm would provide approximately 85% power to detect a 20% reduction in the number of acute care utilizations under individual randomization, assuming the number of encounters follows a Poisson distribution for rare events. The sample size will be inflated based on two parameters: the cluster size coefficient of variation and the intra-class correlation (ICC).⁵⁴ The cluster size coefficient of variation observed among the 14 participating clinical sites is 55%. Therefore, the coefficient of variation is assumed to be 60% and the ICC is assumed to be 0.05.⁵⁶ Based on these parameters, a minimum of 183 EA-SCD participants per arm (366 total EA-SCD participants) will retain approximately 85% power. To account for potential missing data and allow for robust evaluation of secondary endpoints the sample size will be increased to a total of 537 EA-SCD participants. It is estimated that this enrollment can be accomplished with an enrollment rate of 35% of the EA-SCD patient population.

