10.5.4 Primary Analysis

To evaluate the impact of PM, the acute care utilization rate per year will be compared between the PM+STE and STE arms. This will be accomplished using generalized linear mixed model with a Poisson distribution-log link construct. The model will include fixed effects for baseline acute care visits per year, the stratification factor (large sites vs small sites) and treatment arm, and a random effect for clinical site. Corresponding 95% confidence intervals will be calculated for the estimated ACU rate in each treatment arm.

Supportive and sensitivity analyses will be conducted to include potential confounding factors such as urban versus rural sites, education level, older first degree relative with SCD, genotype, age at transfer to adult care, and type of receiving provider (primary versus specialty). Univariate models will be fit for each factor, and those identified to be individually prognostic will be included in a multivariable model, and backward elimination followed by forward selection will be used to identify factors that are independently prognostic and to establish a final base model. Finally, treatment arm will be added to the base model to evaluate the impact of the intervention adjusting for significant baseline factors.

Two analyses will be conducted to estimate the impact of differential accrual between arms over time: (1) An additional term of year of enrollment will be added to the GLMM as a categorical variable; (2) We will subset the analyses to EA-SCD who were contemporaneously enrolled. Comparison of the PM+STE and STE ACU estimates from this subset to those results including all enrolled with and without controlling for year of enrollment will provide a comprehensive assessment of the potential bias due to differential accrual between arms over time. ACU rate in the STE only arm will be compared to historical ACU rates which were used for the original power calculations. Although these are comparisons to historical controls, this will provide preliminary evidence using a robust sample size of the potential impact of the structure transition education.

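### Section 10.5.7 judges consistency of the effect across site size by eye only, with no interaction estimate or interval for the randomisation stratum

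*Combined protocol and SAP*

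**What the plan says.** Section 10.5.7 of the combined protocol and SAP opens with its aim: "We will evaluate the consistency of the intervention across site and patient level characteristics". It names two site-level factors, cluster size and urban versus rural location, and plans subgroup analyses at each level of every factor. The judgement is then described: "Evaluation of the HTE will be performed qualitatively by comparing the treatment group differences across the factor levels". The more formal step that follows is confined to subject-level factors: "each subject-level factor will be evaluated using models to include treatment arm, the baseline factor, and the treatment by factor interaction".

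Site size has a special place in this design. Section 4.2 stratifies the randomisation on it, and section 10.5.4 carries it in the primary model: "The model will include fixed effects for baseline acute care visits per year, the stratification factor (large sites vs small sites) and treatment arm", together with a random effect for site. It enters there as a main effect; no arm-by-size term is named anywhere.

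Urban versus rural is less clear. Section 10.5.7 calls it a site-level factor, but takes its subject-level factors from the multivariable list in section 10.5.4, and that list includes urban versus rural sites.

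**The concern.** An aim of assessing consistency calls for an estimate of how far the effect differs between levels, with its uncertainty. For site size the plan yields two separate subgroup results and an impression. There is no interval for the difference and no rule for reading it, so two careful readers of the same output could reach opposite conclusions.

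The error can go either way. If mentoring worked only at large sites, a reader could overlook that because the small-site interval is wide. If it worked equally at both, a reader could infer effect modification because one subgroup reaches significance and the other does not. Nothing in section 10.5.7 guards against either reading.

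**Working it through.** **The plan's own figures.** Section 10.2 states that "67 EA-SCD participants per arm would provide approximately 85% power", "assuming the number of encounters follows a Poisson distribution for rare events", for a fall from 6 to 4.8 visits a year at two-sided alpha 0.05.

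- Individual randomisation: (1.960 + 1.036)² × (6 + 4.8) / 1.2² = 67.3 per arm.
- Inflation for 7 clusters per arm, ICC 0.05, cluster-size CV 0.60: 67 × 0.95 / (1 − 67 × 0.05 × 1.36 / 7) = 182.3, so 183 per arm.

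Both agree with the document. It gives no power or precision for any subgroup or interaction.

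**Subgroup sizes.** The synopsis gives 8 large and 6 small sites, 80% of participants from large sites, and 537 in total: 0.80 × 537 = 430 and 0.20 × 537 = 107. I assume 4 large and 3 small sites per arm.

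**Interval for the difference, two-year basis.** Mean rate (6 + 4.8)/2 = 5.4 a year over 2 years, Poisson. Between-site SD: √(0.05 × 6)/6 = 0.09 on the relative scale. The variance of a subgroup log rate ratio is 4/(5.4 × 2 × n) + 2 × 0.09²/(sites per arm).

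- Small: 4/(10.8 × 107) + 2 × 0.0081/3 = 0.0035 + 0.0054 = 0.0089.
- Large: 4/(10.8 × 430) + 2 × 0.0081/4 = 0.0009 + 0.0041 = 0.0049 (unrounded parts).
- SE of the log ratio of rate ratios: √0.01377 = 0.117.
- 95% interval if the two observed effects are identical: exp(±1.96 × 0.117) = exp(±0.230) = 0.79 to 1.26.
- A 20% reduction in one stratum and none in the other is a ratio of 1/0.80 = 1.25, or 0.223 on the log scale. The half-width of 0.230 exceeds it. With t on 10 degrees of freedom (14 sites less 4 arm-by-stratum cells) the half-width is about 0.26.

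**Same interval, one-year basis.** The plan's sample size uses one year of visits. The variance per stratum is then (1/6 + 1/(6 × RR))/n per arm × [1 + ((1 + CV²)m − 1) × 0.05], with 53.7 per arm in 3 small sites, 214.8 per arm in 4 large sites, m the mean number per site, and within-stratum CV from 0 to 0.6. With RR 0.80 in both strata the SE of the difference is 0.139 to 0.152. The interval around equal effects is exp(±1.96 × 0.139) = 0.76 to 1.31, widening to exp(±1.96 × 0.152) = 0.74 to 1.35.

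**What a reader by eye might conclude.** Same one-year basis, true RR 0.80 at large sites and 1.00 at small sites. The chance of reading the effect as consistent depends on the informal rule:

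| Informal rule for calling the effect consistent | Chance |
|---|---|
| The two 95% intervals overlap | 86–89% |
| Small-site estimate is below 1 | 50% |
| Small-site estimate is below 0.90 | 16–18% |
| Small-site benefit is at least as large as the large-site benefit | 5–6% |

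**The opposite error.** With a true RR of 0.80 in both strata, power is 0.70 to 0.80 at large sites and 0.44 to 0.50 at small sites. Significance at large but not small sites then occurs with probability 0.80 × (1 − 0.502) = 0.40, or 0.702 × (1 − 0.442) = 0.39.

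**What an interaction test would achieve.** For RR 0.80 against 1.00, a 5% test has 33–39% power with a normal reference and 28–33% with t on 10 degrees of freedom (one-year basis). On the two-year basis, with a normal reference, it has 48%. At ICC 0.05, adding participants at the same 14 sites cannot raise power above about 60% (normal) or 51% (t).

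**Sensitivity to dispersion.** Section 1.1 reports 5.3 ± 8.5 visits a year in the oldest age group at one health system. Using that spread in place of the Poisson variance, one year and unadjusted for baseline, interaction power falls to 7–9%.

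**The case against.** The strongest objection is that a formal test would do little better. With 14 sites, the added interaction test would itself miss the 0.80-versus-1.00 difference in 61–72% of trials on the one-year basis. This stands: the shortage is of sites, and no change of analysis supplies them. The gain from the fix is an honest interval, not power.

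A reader might go further and infer that an effect absent at small sites would usually be missed and reported as consistent. The documents do not support that. Section 10.5.7 has no decision rule and nowhere says that an unclear comparison will be called consistent. As the table shows, the chance of overlooking the difference by eye runs from about 5% to 89% according to how the results are read. The 61–72% is a property of the interaction test and not of the planned comparison.

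Three further objections stand in part:

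- Urban versus rural may already receive an interaction through the list in section 10.5.4, so the clear gap is site size alone.
- The terms listed for the subject-level models need not be exhaustive. It would be too much to say that baseline visits, stratum and the site effect are dropped; the text only leaves it open.
- The section is exploratory, and no passage ties a subgroup result to a recommendation. The synopsis also says that the mentoring comparator can no longer be assessed quantitatively as first planned, so 430 and 107 may not be reached. Smaller numbers would widen the intervals.

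**Conclusion.** The point holds for site size. The plan sets out to assess consistency across the factor on which it stratified the randomisation, yet provides no interaction estimate, no interval and no rule of interpretation. The by-eye comparison can mislead in either direction, including significance at large sites only in about 40% of trials when the true effects are identical.

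The data cannot establish consistency at the scale of the 20% target: even with identical observed effects the interval is about 0.79 to 1.26 in the favourable case and 0.74 to 1.35 at the wide end of the plan's one-year basis. These figures assume Poisson counts, ICC 0.05, full enrolment of 537 with the 80/20 split, 4 + 4 large and 3 + 3 small sites, and normal approximations. They make no allowance for baseline adjustment, which would narrow the intervals, or for overdispersion, which would widen them. They also ignore the constraint in section 4.2 that places two health systems' sites in the same arm.

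This is a desirable improvement to an exploratory analysis and does not affect the primary comparison.

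**What to change.** In section 10.5.7:

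1. Add an arm-by-site-size term to the primary model of section 10.5.4, keeping baseline acute visits, the size stratum and the site random effect. Use small-sample degrees of freedom based on the 14 sites. Report the ratio of rate ratios with its 95% interval.
2. State that the subject-level interaction models use the same base model.
3. Say whether urban versus rural is treated as site-level or subject-level, and estimate its interaction in the same way.
4. State that neither a non-significant interaction nor overlapping subgroup intervals will be described as consistency.
5. Keep the subgroup estimates as a descriptive display.

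I would not add a rule that consistency requires the interval to lie within 0.80 to 1.25. For site size the half-width of 0.230 already exceeds the 0.223 available, so the rule could not be met even by identical estimates.

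The cost is a few sentences and a few model terms, with no new data. The downside is that the site-size result will probably have to be reported as inconclusive.

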10.5.8 Qualitative Methods

Participants will be asked for permission to contact them for future qualitative research related to the ST3P-UP Study. Future research will be approved separately through Georgia Southern University. Participant information will be kept confidential and will only be provided to authorized personnel.

10.5.9 Interim Analysis

A planned interim analysis of primary and secondary endpoints, as well as QI data will take place in year 3. The study is designed with no formal stopping rules and no alpha spend

will occur. The interim analysis will be in support of the interim progress report. We estimate that the interim analysis will include 60% of the total enrollment and the median follow up time for subjects included in the interim analysis is estimated to be approximately 11 months.

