	process outcomes, quality improvement, and impact through eliciting descriptions of participant experiences with one-to-one peer mentoring since we are unable to quantitatively assess the Standard Education + Peer Mentoring comparator as originally planned within the ST3P-UP Study.
STUDY DESIGN	This is a cluster randomized study comparing the effectiveness of adding virtual peer mentoring to a structured education-based transition program based on the Six Core Elements of transition in improving acute care reliance, quality of life and satisfaction with transition process in EASCD. The study will involve 14 clinical sites with a 1:1 randomization at the site level. A total of 537 EA-SCD between the ages of 16 and 25 years who are currently receiving care in a pediatric SCD program will be enrolled and followed prospectively for at least 6 months in pediatrics and at least 24 months in adult care. We will use rapid cycle PDSA improvement methods to implement the structured education-based program in adherence to the 6 core elements and measure adherence to these practice guidelines over time.
OBJECTIVES	 Primary Objective: Compare the effectiveness of STE+PM versus STE at decreasing the number of acute care visits per year over a 24-month period among EA-SCD. Secondary Objectives: To compare the effectiveness of STE+PM versus STE at improving patient- reported outcomes (PROs) among EA-SCD. To compare the effectiveness of STE+PM versus STE at reducing healthcare utilization among EA-SCD.
	 Qualitative Objectives: Identify the facilitators and barriers to enrollment of EA-SCD and mentors from multi stakeholder perspectives Assess mentor-mentee experiences with one-to-one peer mentoring Assess site experiences with the implementation of Quality Improvement methods within their clinical practices Determine the effect of engagement activities on communication within the site triad (adult/pediatric physicians, CBOs, patients) Develop a definition of transition success across the triad (adult/pediatric physicians, CBOs, and patients)
KEY INCLUSION CRITERIA	 Any Sickle Cell Disease genotype Age 16 – 25 years receiving care in a pediatric sickle cell program Able to complete all study procedures with reasonable accommodations

[figure not shown]

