This will be a cluster-randomized study involving 14 clinical sites with randomization occurring at the site level. All clinical sites will implement a structured education-based transition program (STE) that will be implemented across all sites using quality improvement methodology. Implementation of this STE program will be monitored for adherence to QI process and for improvement in clinical outcomes over the 5 years of the study with the goal to fully implement the standard process within the first 18-24 months and allow for 24 months of ongoing follow up. EA-SCD participants will be enrolled while still in pediatrics and must spend a minimum of 6 months and maximum of 12 months in pediatrics to allow them to benefit from the STE intervention prior to transfer to adult care where this intervention will continue. Sites will be randomized 1:1 to receive peer mentoring or no peer mentoring [PM]. Mentoring will occur through a virtual platform and include structured frequent contacts between mentor and mentee for a minimum of 30 months. Primary outcome measures include acute care reliance (reductions in acute care visits and admissions and increase in ambulatory preventative care). Secondary outcomes include improvements in transition readiness, quality of life measures including social support, dexterity with self-care, satisfaction with transition experience for EA-SCD participants and providers, and improvements in quality of care experienced.

Rationale for Structured Education Based Transition Program [STE]:

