5. STUDY PLAN

See Schema (page IV).

This multi-site, cluster randomized trial is designed to compare the effectiveness of transition programs that comprise of structured education-based transition program plus peer mentoring to structured education-based transition program alone in improving acute care reliance among EA-SCD. Using rapid cycle PDSA we will implement standardized transition processes within clinical practices in adherence to the Six Core Elements of transition as positioned by the Got Transition / Center for Healthcare Transition Improvement over 18 - 24 months.

Version 6: 12/22/2022

The combination [STE+PM] intervention will be evaluated to determine if it results in a reduction of acute care reliance among EA-SCD and improves patient reported outcomes as measured by validated tools specific to the SCD population.

This study will last 5 years and includes at least 24 months of QI work to implement the Six Core Elements of transition within pediatric and adult SCD practices. Enrolled subjects will be tracked longitudinally for a minimum of 6 months in pediatrics to a minimum of 24 months in adult care to determine the impact of adding PM to standard education-based transition programming on clinical outcomes.

Enrollment in this study is voluntary and will not impact clinical care. ALL subjects seen at study sites may benefit from the QI work that will be offered, regardless of enrollment status on this study.

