7. REMOVAL OF SUBJECTS FROM STUDY

7.1 Off Study

Subjects may stop their participation in this study at any time if they no longer wish to participate, or if the investigator believes this to be in the best interest of the subject. When subjects are removed from the study, the reason for study removal and date the subject was removed should be documented in the ST3P UP REDCap database. Reasons a subject may be removed from study include, but are not limited to:

- Subject non-compliance with study participation, in the opinion of the investigator
- The subject or legal representative (such as a parent or legal guardian) withdraws study consent
- The subject is lost to follow-up
- Study completion
- Investigator's decision to withdraw the subject
- Subject death

Subjects who have been lost to follow-up for a period without three documented follow up attempts, should be transitioned off study due to lack of compliance with the study required visits per protocol. The off-study date should be documented in the EDC as the day the PI deems the subject as coming off study. This date must correlate with the end of available utilization data after every effort has been made to collect and enter available utilization and survey data. In the event of discrepancy between the documented consecutive attempts to reach the patient and utilization data, please review the data with the DCC PIs to ensure the most appropriate date for

lost to follow up is documented. HIPAA guidelines must be followed. A copy of all communication sent to the subject will be maintained in the research chart.

Subjects that are off study will not participate in future or additional study-related procedures, including data collection.

Subjects who remain enrolled at the completion of the funded project will be off study on the date of study completion.

Subjects that are consented (but not enrolled on study) and withdraw participation will not be required to complete the end of study CRF. Documentation of study withdrawal should be maintained in the research chart.

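### The 30-month minimum follow-up does not fit the 5-year study length and the enrolment projected at the interim: at constant accrual about 24–56% of participants could not reach it, and about 7–40% could not reach 24 months

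*Combined protocol and SAP*

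**What the plan says.** - **Minimum follow-up.** The synopsis (Study Design) says participants will be "followed prospectively for at least 6 months in pediatrics and at least 24 months in adult care". Section 5 repeats it as a "minimum of 6 months in pediatrics to a minimum of 24 months in adult care". Section 1.2 says mentoring will "include structured frequent contacts between mentor and mentee for a minimum of 30 months".
- **Length and common end.** Section 5: "This study will last 5 years". Section 7.1: "Subjects who remain enrolled at the completion of the funded project will be off study on the date of study completion".
- **Projected accrual.** Section 10.5.9 places an interim analysis of the primary and secondary endpoints, "as well as QI data will take place in year 3". It adds: "We estimate that the interim analysis will include 60% of the total enrollment", with a median follow-up of about 11 months. The month within year 3, the accrual curve and the last-enrolment date are not given.
- **Endpoint and population.** Section 10.3.1 divides all acute care visits on study by months on study and multiplies by 24. The secondary version multiplies by 12. Section 10.4 analyses every enrolled participant, with no minimum time on study.
- **Model.** Section 10.5.4 specifies a Poisson mixed model with a log link, adjusted for baseline visits, site size and arm, with a random site effect. It names neither a person-time offset nor a time-since-enrolment term. It adds two sensitivity analyses on "the impact of differential accrual between arms over time": a year-of-enrolment term, and a subset enrolled contemporaneously.

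**The concern.** If everyone leaves the study at month 60, a participant enrolled after month 30 cannot have 30 months of follow-up, and one enrolled after month 36 cannot have 24. With 40% of participants still to enrol at some point in year 3, many would fall on the wrong side of one or both limits.

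Two things are at stake. First, a stated design property, the minimum follow-up, is not delivered by the plan's own figures. Second, the primary endpoint extrapolates short records as if the visit rate were constant, whereas Section 1.1 reports emergency visits and admissions doubling around transition. Every participant starts in pediatrics, so a short record gives relatively more weight to the earlier, lower-rate period. If one arm accrues later than the other, this can create a difference between arms without any treatment effect.

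**Working it through.** **Calculated design figures (Section 10.2).** Individual randomization: (1.960 + 1.036)² × (6 + 4.8) / 1.2² = 67.3 per arm (67 stated). With 7 sites per arm, ICC 0.05 and coefficient of variation 0.60: 7 × 67 × 0.95 / (7 − 67 × 0.05 × 1.36) = 182.3 per arm (183 stated). Both reproduce, and the point below does not depend on them.

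**Latest enrolment months.** For 30 months: 60 − 30 = month 30. For 24 months: 60 − 24 = month 36.

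**Accrual implied by Section 10.5.9.** Under constant accrual, a median follow-up of 11 months means that the included participants enrolled over 2 × 11 = 22 months. The rate is 60% / 22 = 2.73% per month (322 / 22 = 14.6 participants). The remaining 40% (215) takes 40 / 2.73 = 14.7 months. The share enrolled after month t is (last-enrolment month − t) × 2.73%.

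| Interim at month | Last enrolment | Shortest follow-up | Cannot reach 30 months | Cannot reach 24 months |
|---|---|---|---|---|
| 24 | 38.7 | 21.3 months | 23.6% (127) | 7.3% (39) |
| 30 | 44.7 | 15.3 months | 40.0% (215) | 23.6% (127) |
| 36 | 50.7 | 9.3 months | 56.4% (303) | 40.0% (215) |

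**If accrual speeds up after the interim.** With the interim at month 24, the last 40% would have to enrol in 6 months: 6.67% per month, or 6.67 / 2.73 = 2.4 times the earlier rate. At 1.5 times, the share short of 30 months is 15.5% / 40% / 56.4% and the share short of 24 is 0% / 15.5% / 40% for an interim at month 24 / 30 / 36. With the interim at or after month 30, no acceleration brings the share short of 30 months below 40%.

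**If data are cut at month 57.** At constant accrual the ranges become 32–65% short of 30 months and 15–48% short of 24.

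**Size of a possible bias between arms (illustration).** Assume 9 pediatric months for everyone (the middle of the 6–12 in Section 1.2), 2.1 visits per year in that time and 4.2 afterwards. These rates are the Section 1.1 figures for ages 16–18 and 19–21, borrowed here for pediatric and adult time. A participant followed F months (F ≥ 9) has an annualized rate of [9 × 2.1 + (F − 9) × 4.2] / F = 4.2 − 18.9 / F. For F below 9 the rate is 2.1. Averaged over follow-up uniform from a to b (both at least 9), this is 4.2 − 18.9 × ln(b/a) / (b − a).

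Example, interim at month 30:
- Reference arm, F from 15.3 to 52: 3.571.
- Arm enrolling 6 months later, F from 9.3 to 46: 3.378.
- Difference: 1 − 3.378 / 3.571 = 5.4%.

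| Lag of one arm | Mean of individual rates, interim at 24 / 30 / 36 | Weighted by person-time |
|---|---|---|
| 3 months | 1.4% / 2.3% / 4.0% | 1.0% / 1.5% / 2.1% |
| 6 months | 3.1% / 5.4% / 8.0% | 2.3% / 3.3% / 4.2% |

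The range is about 1–8%, against a target effect of 20%.

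**The case against.** The strongest reply is that the shares depend on things the plan does not state: the interim month, the shape of accrual and when recruitment stops. That stands, so the shares are conditional. A lag between data cut and analysis would also mean that more than 60% had enrolled by the analysis date, so the interim month above is best read as the cut-off month. None of this removes the conflict; it shows why a last-enrolment date is needed.

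A second reply is that the analysis is of a rate, so multiplying by 24 or by 12 cancels in the ratio between arms, and variable follow-up is openly allowed for. This is correct, but the constant-rate assumption remains whichever multiplier is used. A third is that the year-of-enrolment and contemporaneous-subset analyses address this mechanism. With a common end date, year of enrolment largely fixes the maximum follow-up, so they do reduce the concern. They are sensitivity analyses, however, and change neither the stated minimum nor the scaling.

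Four stronger readings are tempting and are not supported:

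- *That 24–56% have an extrapolated 24-month endpoint.* That is the share short of 30 months. Only those short of 24 months (7–40%) are scaled up.
- *That the minimum simply cannot be met.* This is absolute only for an interim at or after month 30.
- *That short records are mostly pediatric.* With pediatric time uniform over 6–12 months, only 0.8% / 8.5% / 23.6% of participants have more than half their follow-up in pediatrics (interim at month 24 / 30 / 36).
- *That the bias is 12–26%.* Under the same assumed rates, one person followed 30 months has 3.57 visits per year, one followed 18 months 3.15 (12% lower) and one followed 12 months 2.63 (26% lower). These are contrasts between individuals, not between arms, and at constant accrual nobody has as little as 12 months unless the interim is late in year 3.

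Nor do the documents say which arm accrues later. The mentoring arm is the plausible one, since Section 10.1.2 enrols its participants only after a mentor match and Section 3.2.1 foresees delays in matching.

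**Conclusion.** The point holds as an inconsistency that should be corrected. The stated minimum follow-up, the 5-year length with a common end, and the interim projection do not fit together at a constant accrual rate, wherever in year 3 the interim falls. The shares in the first table rest on constant accrual, a month-60 end and no dropout. Dropout or an earlier cut would raise them; faster late accrual would lower them, within the limits shown.

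The consequence for the primary endpoint is real but moderate: a constant-rate extrapolation for those under 24 months, and a possible spurious difference of about 1–8% if one arm accrues 3–6 months later. That second figure is an illustration, resting on age-band rates used as rates by care setting and on equal pediatric time in both arms. It should not be read as an estimate of the bias in this trial.

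**What to change.** 1. State a last-enrolment month consistent with the minimum follow-up, or restate the follow-up that can be achieved. Reconcile the synopsis, Sections 1.2 and 5, and Section 10.5.9. The mentoring duration in Section 1.2 has to be reconciled with the same dates. Give the month of the interim data cut.
2. Define the primary endpoint as the count of acute care visits in the first 24 months after enrolment, and analyse it in the Section 10.5.4 Poisson mixed model with log person-time as an offset.
3. Add a time-since-enrolment term, or a pediatric/adult period term, at least as a sensitivity analysis. The offset handles unequal length of follow-up but still assumes a constant rate; this term relaxes that assumption. The utilization data collected every 3 months (Section 6.4.3) are sufficient.
4. Keep the year-of-enrolment and contemporaneous-subset analyses.

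The cost is protocol and SAP wording and a modest change to the analysis dataset. If follow-up is restated, the minimum becomes less favourable. Visits after month 24 leave the primary endpoint, though they remain in the secondary endpoint over the entire study.
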